5.3.2 Cisplatin Dose Modifications

There is one level of dose reduction for cisplatin (dose level -1): when dose reduction is required, cisplatin will be reduced to 30 mg/m²/week. There is no dose level below 30 mg/m². Retreatment criteria for pembrolizumab and cisplatin are independent. Dose modifications for cisplatin are specified for hematologic and non-hematologic toxicity in Tables 6 and 7 below.

Table 6. Cisplatin Dose Modifications for Hematologic Toxicity

NCI CTCAE Toxicity Grade (CTCAE v. 4)	Cisplatin Dose ^{c,d} at Start of Subsequent Cycles of Therapy
Neutropenia	
1 (1500-1999/mm³)	Maintain cisplatin dose level
2 (1000-1499/mm³)	Maintain cisplatin dose level
3 (500-999/mm³)	Hold cisplatin dose for the week; check CBCD weekly. Resume cisplatin at dose level -1 (30 mg/m ² /week) when neutropenia recovers to Grade 2 or better.
4 (<500/mm³)	Hold cisplatin dose for the week; check CBCD weekly. Resume cisplatin at dose level -1 (30 mg/m ² /week) when neutropenia recovers to Grade 2 or better.
Second incident, grade 3-4 neutropenia	Hold cisplatin and recheck CBCD weekly. Resume cisplatin at 30 mg/m ² /week when neutropenia reaches Grade 2 or better.
Neutropenic Fever^e	Hold cisplatin and initiate standard treatment. Resume cisplatin at 30 mg/m ² /week when neutropenia has recovered to Grade 2 or better, neutropenic fever has resolved, and patient is stable.
Thrombocytopenia	
1 (75,000/mm³-LLN)	Maintain cisplatin dose level
2 (50,000- 74,999/mm³)	Hold cisplatin dose for the week; check CBCD weekly. Resume cisplatin at dose level -1 (30 mg/m ² /week) when thrombocytopenia recovers to Grade 1 or better.
3 (25,000- 49,999/mm³)	Hold cisplatin dose for the week; check CBCD weekly. Resume cisplatin at dose level -1 (30 mg/m ² /week) when thrombocytopenia recovers to Grade 1 or better.
4 <25,000/mm³)	Hold cisplatin dose for the week; check CBCD weekly. Resume cisplatin at dose level -1 (30 mg/m ² /week) when thrombocytopenia recovers to Grade 1 or better.
Second incident, grade 2-4 thrombocytopenia	Hold cisplatin and recheck CBCD weekly. Resume cisplatin at 30 mg/m ² /week when thrombocytopenia reaches Grade 1 or better.

Table 7. Cisplatin Dose Modifications for Non-hematologic Toxicity

NCI CTCAE Toxicity ^a Grade (CTCAE v. 4)	Cisplatin Dose ^b
Renal-serum Creatinine	
≤ Grade 1 (ULN-1.5 x ULN)	Maintain cisplatin dose level
Grade 2 (> 1.5-3.0 x ULN)	Hold cisplatin. Check serum creatinine weekly. Resume cisplatin at dose level -1 (30 mg/m ² /week) when recovered to Grade 1 or baseline.
≥ Grade 3 (>3.0-6.0 x ULN) ^c	Discontinue cisplatin. Per investigator discretion, the patient may be changed to carboplatin AUC 2 weekly.
Fatigue	
Grade 3	Decrease cisplatin to dose level -1 (30 mg/m ² /week)
Nausea/Vomiting	
≤ Grade 2 with maximal medical management	Maintain dose level
≥ Grade 3 with maximal medical management	Hold cisplatin until ≤ grade 2, then resume cisplatin at dose level -1 (30 mg/m ² /week)
Other non-hematologic Toxicities^d	

Neuropathy Grade 2 Grade 3-4	Decrease cisplatin to dose level -1 (30 mg/m ² /week) Discontinue cisplatin. Per investigator discretion, the patient may be changed to carboplatin AUC 2 weekly.
Ototoxicity Grade 2 Grade 3-4	Decrease cisplatin to dose level -1 (30 mg/m ² /week) Discontinue cisplatin
Other: Mucositis in RT field Grade 0-3 Grade 4	Maintain cisplatin dose level Hold cisplatin until \leq grade 3, then resume at dose level -1 (30 mg/m ² /week)
Rash , in RT field (inclusive of radiation dermatitis) Grade 2-3 Grade 4	Maintain dose level ^d Hold cisplatin until \leq grade 3, then resume at dose level -1 (30 mg/m ² /week)
Rash , out of RT field Grade 1-4	Maintain cisplatin dose level
Grade 3-4/Other ^e	Hold cisplatin until baseline or \leq grade 1; per investigator judgment, may resume cisplatin at dose level -1. Note exceptions in footnote. ^f

^aFor CTCAE Grade \leq 2 non-hematologic toxicity not described above, attributed to cisplatin, maintain dose level of cisplatin.

^bDose levels are relative to the previous dose. Dose reductions of cisplatin below the -1 dose level will not be allowed. For a second incident of non-hematologic toxicity of sufficient severity to require dose modification, hold cisplatin until toxicity resolves to Grade 1 or baseline, then resume at 30 mg/m²/week.

^cIf Grade \geq 3 nephrotoxicity occurs,

^dDose modification of cisplatin is not required in the setting of asymptomatic electrolyte abnormalities. For depressed K or Mg, administer replacement therapy per local standard. Cisplatin may continue at full dose, at the discretion of the treating physician.

^ePer investigator discretion, cisplatin may be dose-reduced to dose level -1 or held for grade 3 radiation dermatitis.

^fFor CTCAE Grade 3-4 non-hematologic toxicity not described above, attributed to cisplatin, hold cisplatin until baseline or \leq Grade 1. Per investigator judgment, may resume cisplatin at dose level -1.

^fCisplatin does **not** need to be held or dose-reduced for grade 3 dysphagia, grade 3 pain, grade 3 weight loss, or grade 3 fatigue, which are expected toxicities for chemoradiation of HNSCC and will be managed aggressively by treating investigators per standards of care.

If ototoxicity or nephrotoxicity occurs, treatment can be changed to carboplatin with AUC (area under curve) of 2 for remainder of concurrent radiotherapy.

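### Table 7 requires a cisplatin reduction for grade 3 fatigue that the table's own exception footnote waives

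*Combined protocol and SAP*

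**What the plan says.** Section 5.3.2 makes its tables the governing rules: "Dose modifications for cisplatin are specified for hematologic and non-hematologic toxicity in Tables 6 and 7 below". It allows a single reduction step for cisplatin, to dose level -1.

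Table 7 (non-hematologic toxicity) gives fatigue its own row. For Grade 3 the instruction is "Decrease cisplatin to dose level -1", that is, 30 mg/m² per week. The row has no discretion clause and, in the text available, no footnote mark.

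Further down, the catch-all row for other grade 3-4 toxicities tells sites to hold cisplatin until recovery, and continues "per investigator judgment, may resume cisplatin at dose level -1. Note exceptions in footnote". The exception footnote states that cisplatin does not "need to be held or dose-reduced for grade 3 dysphagia, grade 3 pain, grade 3 weight loss, or grade 3 fatigue". Its reason is that these are events "which are expected toxicities for chemoradiation of HNSCC and will be managed aggressively by treating investigators per standards of care".

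Footnote b to the table adds a rule for a second non-hematologic toxicity severe enough to require dose modification: cisplatin is held until Grade 1 or baseline, then resumed at 30 mg/m² per week.

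**The concern.** The same event meets two different instructions within one table. Two sites could manage identical patients differently, each pointing to the protocol.

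Two further matters then have no clear answer. The first is whether a site that keeps the dose has committed a protocol deviation. The second is whether grade 3 fatigue is a first incident for footnote b, which determines how a later toxicity is handled.

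The case is unlikely to be purely theoretical. The footnote itself calls grade 3 fatigue expected with chemoradiation, and both arms receive the same cisplatin-IMRT backbone.

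**Working it through.** **The texts side by side, for grade 3 fatigue**

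| | Fatigue row, Table 7 | Exception footnote, Table 7 |
|---|---|---|
| Action on cisplatin | Reduce to level -1 | Neither hold nor reduction needed |
| Force | Directive | Permissive |
| Called from | Stands alone | The row for other grade 3-4 toxicities |

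| Site's action | Under the row | Under the footnote |
|---|---|---|
| Reduces | Complies | Complies |
| Keeps the dose | Departs | Complies |

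The conflict is confined to the site that keeps the dose.

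**Knock-on through footnote b.** The footnote b rule turns on whether the earlier toxicity required a dose modification. Under the Fatigue row, grade 3 fatigue did; under the exception footnote, it did not. Suppose the patient later develops Grade 2 neuropathy. As a first incident, Table 7 calls for a reduction to level -1. As a second incident, footnote b calls for a hold until Grade 1 or baseline. Which applies depends on the unresolved question.

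**Size per affected patient.** Inputs: starting dose 40 mg/m² weekly (Section 5.2.2), seven doses (Section 5.2.3), level -1 = 30 mg/m² (Section 5.3.2). Assume that all seven doses are given, that the reduction lasts to the end, and that the patient was not already at level -1.

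Unreduced: 7 × 40 = 280 mg/m².

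Reduced from week w: 40 × (w − 1) + 30 × (8 − w).

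| First reduced week | Calculation | Cumulative (mg/m²) | Difference from 280 |
|---|---|---|---|
| 2 | 40 + 180 | 220 | 60 |
| 3 | 80 + 150 | 230 | 50 |
| 4 | 120 + 120 | 240 | 40 |
| 5 | 160 + 90 | 250 | 30 |
| 6 | 200 + 60 | 260 | 20 |
| 7 | 240 + 30 | 270 | 10 |

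The range is 10 to 60 mg/m², or 10/280 = 3.6% to 60/280 = 21.4% of the unreduced total. For a patient already at level -1 because of another toxicity, the difference is zero.

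**Number of patients affected.** This cannot be derived. Section 5.4.13 gives a frequency for grade 3 mucositis and dysphagia, but lists fatigue without a grade or a rate.

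**The case against.** **Scope.** The exception footnote is called from the catch-all row, so it may qualify only that row's hold rule and leave the specific Fatigue row in force. This is a reasonable reading, but it does not clear up the text. Fatigue has its own row and so is not an other toxicity; on this reading, naming it in the footnote would do nothing. The footnote also waives dose reduction as well as holding.

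**Permissive wording.** A reader might infer that the two texts cannot both be followed for one patient. The documents do not support that: the footnote does not forbid a reduction, so a site that reduces satisfies both. This objection stands and sets the limit of the point.

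**Extraction.** The footnote letters under Table 7 look misaligned in the text available, with two notes marked f. PDF reading may explain this. The wording of the row and of the exception sentence is complete, and the conflict does not depend on the letters.

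**The pembrolizumab table.** Footnote d to Table 4 carries a similar exception list. It cannot settle the cisplatin rule, because Sections 5.3.1 and 5.3.2 say the retreatment criteria for the two drugs are independent.

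**Consequences.** Section 1.3 stresses a cumulative dose of at least 200 mg/m² and notes that 30 mg/m² throughout still gives 210. Every total in the table above exceeds 200, which limits the importance of the point. That comfort assumes no missed doses: a patient reduced from week 2 who misses one later dose receives 220 − 30 = 190, while an unreduced patient who misses one receives 280 − 40 = 240.

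**Conclusion.** The inconsistency is real and narrow. For grade 3 fatigue, one part of Table 7 requires a reduction that another part says is not needed. What follows from the text is possible inconsistent handling between sites, uncertain deviation coding, and an unclear incident count under footnote b. The cumulative cisplatin difference is 10 to 60 mg/m² per affected patient, on the assumptions stated with the calculation.

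A reader might infer that the conflict confounds the DLT and PFS results. The documents do not support that:

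- Grade 3 fatigue is not on the DLT list in Section 5.7.1, where the general non-hematologic threshold is Grade 4 and the event must be at least possibly related to pembrolizumab.
- The same cisplatin text covers both randomized arms. Unequal application between arms is conceivable in an open-label trial where only Arm 2 gives pembrolizumab alongside cisplatin, but nothing shows it.
- The trial is described as non-comparative. Each arm is judged against fixed thresholds, and the arms are ranked on 1-year PFS only if both pass.
- The sample size, advancement criteria and stopping boundaries do not use this rule.

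This is a wording correction worth making, not a threat to the design. No view is taken here on which instruction is clinically right.

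**What to change.** Reconcile the Fatigue row of Table 7 with the exception footnote so that one instruction applies to grade 3 fatigue in both arms. The clinical team decides which. The revised text should make clear whether the event counts as an incident for footnote b; deviation coding then follows from the single rule. Check the footnote letters under Table 7 in the same edit, so that each row points to the note meant for it. Notify sites.

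The cost is a short protocol correction and a site notice. Sample size, endpoints and analysis are unchanged.

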5.4 Intensity Modulated Radiotherapy (IMRT)

5.4.1 Dose specifications

IMRT will be delivered in 35 fractions over 7 weeks (five fractions per non-holiday week) in one plan (SIB). Concomitant boost using separate IMRT plans is not allowed.

Missed treatments due to holidays or logistic reasons can be compensated for by delivering an additional BID treatment during the week, OR treating on the Saturday or Sunday of that week, OR adding to the end of treatment.

5.4.2 Immobilization and Simulation

Patients must have an immobilization device (e.g. Aquaplast mask) made prior to treatment planning CT scan. Use of an immobilizing mouthpiece is strongly encouraged for all patients, especially those with cancers of the oral cavity and oropharynx.

The treatment planning CT scan should be performed with IV contrast so that the major vessels of the neck are easily visualized. The treatment planning CT scan must be performed with the immobilization device and in the treatment position. Slice thickness should be 0.3 cm or thinner.

5.4.3 Target Delineation

The Gross Tumor Volume (GTV) is defined as all known gross disease determined from CT, PET/CT, clinical information, endoscopic findings and/or potentially MRI.

The Clinical Target Volume (CTV) is defined as the GTV plus areas considered to contain potential microscopic disease, delineated by the treating physician. The margin between each GTV and its CTV will typically be a minimum of 0.5 cm except in those areas where the GTV is immediately adjacent to structures known to be uninvolved such as bone and adjacent muscle. In this instance, the CTV should be modified to exclude structures that serve as a boundary that prevents the natural spread of disease (bone, muscle, etc).

The Planning Target Volume (PTV) will provide a margin around each CTV (i.e. both the primary tumor and the lymph nodes containing clinical or radiographic evidence of metastases) to compensate for the variation of treatment set up and internal organ motion. Studies should be implemented by each institution to define the appropriate magnitude of the uncertainty components of the PTV; however, an unedited expansion of 0.3 - 0.5 cm is recommended.

In general, the PTV should not go outside of the skin surface; if it does exceed the skin surface, the application of bolus material over this portion of the PTV may be considered if it is judged clinically that the skin is at risk but is generally not recommended.

For those institutions that are using daily IGRT for margin reduction, the minimum CTV-to-PTV expansion is 3.0 mm (a larger expansion may be necessary for a target volume subject to significant intra-fraction variability, such as the non-immobilized oral tongue). In general, the CTV-to-PTV expansion (with IGRT) should not exceed 5 mm.

The primary tumor and involved nodes (CTV1) will typically consist of a 0.5 - 1.5 cm expansion of the gross tumor volume (GTV) to cover potential local invasion and will be prescribed 2 Gy/fraction, total 70 Gy (see Section 5.4.8. for details of prescription for PTV1).

High-risk sub-clinical disease sites, which include possible local subclinical infiltration at the primary site (primary site CTV2) and first echelon nodes, which are not clinically or radiographically involved (nodal CTV2), should be expanded by 3 - 5 mm to create PTV2. PTV2 should receive a total dose of 60 Gy/35 fractions.

Lower-risk targets (PTV3) (such as neck nodal levels which are not first echelon nodes and are not adjacent to levels containing grossly involved nodes) will be prescribed 54 Gy/35 fractions

Treatment of the low neck: see details in Section 5.4.7. If the low neck is treated, the preferred technique is to treat with isocentric matching AP or AP-PA fields with larynx block, matched to the IMRT portals just above the arytenoids. The dose will be 2 Gy per fraction prescribed to 3 cm depth to a total dose of 50 Gy in 25 daily fractions. Whole-neck IMRT is allowed. Involved low neck nodes will receive total 70 Gy

in 35 fractions. This can be achieved by either boosting the low neck field with an additional 16 Gy in 8 fractions, by an AP or AP-PA fields, or by planning the whole neck using IMRT. In cases of gross involvement of the vallecula or low neck, whole-neck IMRT should be considered. Whole-neck IMRT may also be considered if level VI is considered to be at risk due to gross involvement of level IV nodes.

All plans must be normalized such that 95% of the volume of the PTV1 is covered with prescription dose of 70 Gy. Additionally: At 1 cc PTV1 volume on the DVH curve, the dose should not be $> 110\%$ of the prescribed dose. At a volume of 0.03 cc within the PTV1 volume on the DVH curve, the dose should not be $< 95\%$ of the prescribed dose. For any volume of tissue outside the PTVs that has a size of 1 cc, the dose should not be > 74 Gy.

Lymph Node Regions

- a. Submental nodes (*level IA*): In cases where the floor of mouth, oral tongue, or level IB are involved.
- b. Submandibular nodes (*level IB*): To be covered when the ipsilateral level II has nodal disease of at least 3 cm or the oral cavity is involved.
- c. Upper deep jugular (*junctional, parapharyngeal*) nodes: all cases (*at the neck side ipsilateral to the primary tumor*).
- d. Subdigastric (*jugulodigastric*) nodes, midjugular, lower neck, and supraclavicular nodes (*levels II through IV*): all cases, bilaterally; unilateral neck treatment can be considered for well lateralized T1/2 primary tumors.
- e. Posterior cervical nodes (*level V*): all cases, at the neck side where there is evidence of jugular nodal metastases.
- f. Medial retropharyngeal nodes: all cases involving the pharyngeal axis (i.e. not required for oral cavity and larynx cancers not involving pharyngeal structures) should be contoured from the level of C1 through the superior border of the hyoid body.

Critical Normal Structures

The normal tissue volume to be contoured will include the skin surface, brainstem, spinal cord, mandible, glottic larynx, supraglottis, esophagus, trachea, oral cavity, lips and parotid and submandibular salivary glands. The PRV (planning risk volume) spinal cord contours will be defined at least 0.5 cm larger in the radial dimension than the spinal cord (*i.e. the cord diameter on any given slice will be 1.0 cm larger than the cord itself*). The normal tissues will be contoured and considered as solid organs. The tissue within the skin surface and outside all other critical normal structures and PTVs is designated as unspecified tissue

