5.4.7 Management of the Low Neck/Supraclavicular Region (Match versus No Match)

It is recognized that comprehensive head and neck irradiation incorporating IMRT can be done in several ways, any of which is permitted for this study. Patient-specific QA measurements are required for all IMRT treatments. When a field "match" technique is used for treating the lower neck, patient-specific measurements should include a verification of the dose coverage in the gap region for each patient.

1. Match: The upper cervical lymphatics and primary tumor bed are treated with IMRT. The lower cervical lymphatics and supraclavicular region are treated with a single AP (or occasionally APPA for larger patients with posterior neck at high risk) non-IMRT technique. The latter non-IMRT field(s) is matched to the upper neck IMRT fields. This technique requires comprehensive mid-line spinal cord blocking in the lower neck fields. This technique also allows for a simultaneous blocking of portions of the larynx, hypopharynx, and cervical esophagus in the lower neck fields. Matching 2 IMRT plans is allowed.
2. No Match: The entire clinical target volume (CTV) [upper and lower neck and primary tumor bed] is irradiated with IMRT. There is no match line between upper and lower portions of the regions at risk. In this technique, limiting radiotherapy dose to organs at risk (OARs), e.g., the cervical esophagus, is entirely achieved by inverse treatment planning via IMRT algorithms.

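### The low-neck boost in section 5.4.3 sums to a nominal 66 Gy in 33 fractions, not the 70 Gy in 35 it is said to achieve

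*Combined protocol and SAP*

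**What the plan says.** All the figures in conflict are in section 5.4.3 (Target Delineation).

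- **General prescription.** The primary tumour and involved nodes (CTV1) "will be prescribed 2 Gy/fraction, total 70 Gy".
- **Low-neck field.** When the low neck is treated, matched AP or AP-PA fields are the preferred technique. For these, "The dose will be 2 Gy per fraction prescribed to 3 cm depth to a total dose of 50 Gy in 25 daily fractions".
- **Involved low-neck nodes.** "Involved low neck nodes will receive total 70 Gy", with 35 fractions given as the course.
- **How to reach that total.** Two routes are offered: "boosting the low neck field with an additional 16 Gy in 8 fractions", using AP or AP-PA fields, or planning the whole neck with IMRT.
- **Lower-risk targets (PTV3).** These "will be prescribed 54 Gy/35 fractions".

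Section 5.4.7 describes the matched option. There, nodes of the lower neck together with the "supraclavicular region are treated with a single AP (or occasionally APPA for larger patients with posterior neck at high risk) non-IMRT technique". It gives no other dose for that field.

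**The concern.** The boost route is presented as delivering 70 Gy in 35 fractions, but the base and boost given in the same paragraph do not add up to that. A planner who takes the base and boost figures at face value prescribes less to gross disease than the protocol intends, and finishes two fractions early.

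The instruction belongs to the technique that the protocol prefers for the low neck. Local failure at 1 year is one of the three criteria for advancing an arm (section 9), so the dose to gross disease should not be open to two readings.

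**Working it through.** **Inputs (all from section 5.4.3)**

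| Item | Dose | Fractions | Gy per fraction |
|---|---|---|---|
| Low-neck base field | 50 Gy | 25 | 50/25 = 2.00 |
| Boost | 16 Gy | 8 | 16/8 = 2.00 |
| Stated total, involved low-neck nodes | 70 Gy | 35 | 70/35 = 2.00 |
| PTV3, lower-risk targets | 54 Gy | 35 | 54/35 = 1.54 |

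**Step 1. Try to reproduce the stated total.**
- Dose: 50 + 16 = 66 Gy, against 70 Gy.
- Fractions: 25 + 8 = 33, against 35.
- Shortfall: 70 − 66 = 4 Gy, and 4/70 = 5.7%; 35 − 33 = 2 fractions; 66/70 = 94.3% of prescription.

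The stated figure is not reproduced in dose or in fractions.

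**Step 2. Find the base that would make the boost sentence true.**
- 70 − 16 = 54 Gy and 35 − 8 = 27 fractions (54/27 = 2.00 Gy each).
- A base of 54 Gy in 27 appears nowhere in the protocol.
- The 54 Gy that does appear is the PTV3 prescription in 35 fractions. At 1.54 Gy per fraction it is not the 2 Gy low-neck field, and adding the boost would give 35 + 8 = 43 fractions.

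**Step 3. Find the boost that would make the base sentence true.**
- 70 − 50 = 20 Gy and 35 − 25 = 10 fractions (20/10 = 2.00 Gy each).

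Changing either number alone restores 70 Gy in 35 at 2 Gy per fraction, so the arithmetic does not show which one slipped.

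**Step 4. Could the prescription depth close the gap?** The matched field is a non-IMRT technique with its dose prescribed at 3 cm, so the dose at a given node differs from the nominal value. Assume the boost is prescribed at the same depth, which the protocol does not state. Tissue then reaches 70 Gy only where the fields deliver at least 70/66 = 106.1% of the 3 cm dose. Depth cannot supply the two missing fractions in any case.

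The same reasoning limits the claim. Section 5.4.8 sets a PTV70 minimum of 66.5 Gy, and 66.5/66 = 100.8%. That margin is too small for a nominal total to settle, so no breach of the minimum is asserted.

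**The case against.** The best defence is that the boost sentence is subordinate to a prescription stated clearly and more than once. The 70 Gy in 35 fractions stands immediately before it. The paragraph that follows requires that "All plans must be normalized such that 95% of the volume of the PTV1 is covered with prescription dose of 70 Gy". For the group concerned, the protocol also points to the technique that avoids the problem: "In cases of gross involvement of the vallecula or low neck, whole-neck IMRT should be considered". On this view, a site would have to overlook the sentence before the boost and the mandatory rule after it, so this is a minor clarification.

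These safeguards are real, and they limit the likely harm. They show which total was intended and let a plan reviewer notice the shortfall. They do not make the boost sentence correct: a worked dose instruction for gross disease still contradicts the total it claims to deliver, and whole-neck IMRT is to be considered, not required.

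A second objection is that 54 Gy in 27 is conjecture. This largely stands. Table 8 (section 5.4.10) lists both 50 and 54 Gy for lower-risk nodal regions, but without fraction counts. Section 5.4.3 already accounts for both values, as the matched field (50 Gy) and PTV3 (54 Gy). Table 8 is therefore weak evidence for a 54 Gy low-neck base, and 50 Gy in 25 is the only base actually written for that field. Asking the radiation oncology lead remains sensible, because the protocol does not settle it.

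**Conclusion.** The concern holds, and the sentence should be fixed. As written, the matched-field boost gives a nominal 66 Gy in 33 fractions against a stated 70 Gy in 35: 4 Gy (5.7%) and 2 fractions short. This is direct addition of figures in one paragraph. It rests only on the boost being added to the low-neck field dose stated there, and no other dose for that field is given.

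The reach is narrow: patients with involved low-neck nodes treated by matched field plus boost. The protocol does not say how many there would be, so no effect on local failure or PFS can be estimated. The instruction is common to both arms, and no between-arm bias is claimed.

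**What to change.** Ask the radiation oncology lead to confirm the intended low-neck base, then correct one number pair in section 5.4.3:

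- **If 50 Gy in 25 is intended:** change the boost to 20 Gy in 10 fractions. 50 + 20 = 70 Gy; 25 + 10 = 35 fractions.
- **If 54 Gy in 27 was intended:** correct the base sentence and keep the 16 Gy in 8 boost. 54 + 16 = 70 Gy; 27 + 8 = 35 fractions.

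The same amendment could reconcile Table 8 with the text. These items are separate, and the conclusion above does not depend on them:

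- **1 cc limit outside the PTVs:** 74 Gy in sections 5.4.3 and 5.4.8 (74/70 = 105.7% of prescription), 63 Gy in Table 8 (63/70 = 90.0%).
- **Oral cavity mean:** below 30 Gy in section 5.4.8, at most 32 Gy in Table 8.
- **OARpharynx mean:** below 45 Gy in section 5.4.8, where it is a non-mandatory goal; at most 40 Gy in Table 8.
- **Larynx mean:** at most 20 Gy for the glottic larynx in section 5.4.8, at most 35 Gy for the glottic/supraglottic larynx in Table 8. These may be different structures.

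The cost is one confirmation, a one-line dose correction and a reconciled table, issued as a clarifying amendment with a memo to sites. Design, sample size and analysis are unchanged.
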